5.6.1.7. Venipuncture

Blood sampling carries the risk of minor discomfort, bruising, fainting and, rarely, infection at the needle puncture site.

5.6.1.8. Mucosal Secretion Collections

Mucosal secretion samples will be collected in the clinic (semen, penile swab, rectal sponges, rectal swab, cervico-vaginal menstrual discs, vaginal swab, endocervical cytobrush/swab) by trained study personnel. Alternately, for the collection of cervical-vaginal secretions, women may elect to insert and remove cervical menstrual discs themselves. For the collection of penile swabs, men may elect to collect the swabs themselves during the study visit. Inserting an

instrument (speculum, anoscope, sponge, swab, menstrual disc, cytobrush) into the anus or the vagina may cause discomfort and slight irritation. There is no evidence of rectal sponge/swab, penile swab, cervical menstrual disc, or vaginal swab sampling contributing to risk of HIV or other sexually transmitted infection. Semen will be collected by masturbation.

Cytobrush/swab collection: A cytobrush/swab is a small flexible plastic instrument with bristles at the tip used in gynecologic procedures to collect cervical cells for subsequent laboratory analysis.

For these mucosal collections, men and women will be asked to refrain from receptive vaginal or anal intercourse, douching, or inserting any product into the rectum or vagina for 3 days prior to the mucosal collection. Men will be asked not to masturbate nor ejaculate for 3 days prior to semen collection.

5.6.1.9. Sigmoid Biopsy

Sigmoid biopsies will be performed with a flexible sigmoidoscope. Brief cramping and gas pains may be felt as air is inserted or as the scope advances. The passing of gas is necessary and should be expected after the procedures are terminated. Participants may choose to receive sedation during the procedure in order to ameliorate the discomfort and anxiety they may feel. There may be slight bleeding from the biopsy site, which generally stops spontaneously. In rare cases, an interventional endoscopic technique is needed to stop bleeding. There is a remote possibility that a biopsy may result in significant bleeding or even perforation requiring emergency medical care. A gastroenterologist will perform this procedure in order to minimize these risks. As a precautionary measure, however, all participants will be counseled to avoid receptive anal intercourse for 3 days prior to and 7 days following sigmoid biopsies.

5.6.1.10. Inguinal Lymph Node Biopsy

The excisional inguinal lymph node biopsy will be performed under local anesthesia by a qualified surgeon. As with all surgical procedures, there is a risk of scarring, bruising, bleeding or infection at the surgical site. These risks are minimized by the small size of the incision (approximately 1-2 centimeters), clinical evaluation to determine any additional bleeding risks (such as anticoagulant use or a congenital clotting disorder), and the adherence by the surgeon to aseptic technique. Participants may experience some discomfort following the procedure despite use of local anesthesia; for participants who complain of any subsequent discomfort, additional analgesia will be made available. There is a possibility of seroma formation at the biopsy site, which may require subsequent drainage and further management, or sensory nerve injury during the procedure, which could result in temporary or permanent local reduction in feeling. There is a small risk of chronic swelling of the leg on the side that the lymph node is taken from. For this reason, it is recommended that one participant have no more than 4 inguinal lymph node biopsies, or 2 biopsies per side, done in the subject's entire life, which would include this study, and any other studies, and any medical procedures performed elsewhere for non-research purposes. Finally, there is the unlikely possibility that the procedure will be unsuccessful and no lymph node will be recovered. This procedure will be performed by trained personnel at Chulalongkorn Hospital in Bangkok, which has a long history of safely performing lymph node biopsies on both HIV infected and healthy individuals (Chintanaphol, 2018). Only a single lymph node biopsy will be performed per participant in this study.

5.6.1.11. Leukapheresis

Adverse reactions to leukapheresis procedure are rare and include vaso-vagal episodes related to needle insertions and transient volume shifts, peri-oral paresthesias, chills, nausea, and heartburn caused by the citrate anticoagulant used during the procedure. Vaso-vagal reactions are handled by postural manipulation and fluid administration. Participants will be observed closely by an experienced blood bank technician or trained medical staff during the procedure. Citrate reactions are usually relieved by slowing the rate of the anticoagulant infusion and by administering oral calcium carbonate tablets. Allergic reactions can occur with the use of chemical during this procedure. There is limited data on allergic reactions with individuals undergoing leukapheresis but the possibility of having anaphylactic reactions cannot be completely eliminated or prevented during the procedure. An emergency cart will be on standby to respond to an allergic reaction if it occurs.

5.6.1.12. Social Harm and Discrimination

In the unlikely event of HIV infection during this study, the primary concern is related to ascertaining and providing HIV diagnostic information and, in particular, involuntary disclosure of HIV status to others. These disclosures may result in depression and rarely suicide among individuals learning that they are infected with the HIV virus. Furthermore, involuntary disclosure to others may result in prejudice by the community, family, employers, and psychosocial factors including stigma and discrimination. This risk will be minimized by the fact that all counselors will be trained in pre- and post-test counseling for HIV and will aim at fully informing participants of all activities in the study and attendant risks and benefits. The candidate vaccines may also induce false positivity to standard HIV antibody tests and may result in problems when applying for life or health insurance, international travel, employment or hospitalization. If there are any problems related to the above situations, the investigators will provide HIV testing to confirm HIV status. They will provide this information to the persons involved. Currently, people who have received experimental HIV vaccines are deferred from blood donation even though they do not have HIV infection.

The study staff will take appropriate action to assist participants with any discrimination they may experience by participating in this study. Such measures will be accompanied with appropriate counseling.

5.6.1.13. Unknown Risks

As with all research there is the possibility of risks that are unknown or that cannot be foreseen based on current information. It is currently unknown whether the vaccination will be effective at attenuating or preventing HIV or if it will affect any future HIV vaccinations.

5.6.2. Alternatives to this IND Product or Study

At this time, there are no known alternatives to these vaccines that afford the same potential protection from acquiring HIV.

5.6.3. Potential Benefit for Participants

Study participants will receive no direct benefit from study participation. Female participants who choose to undergo cervical mucosal samplings may benefit from early detection of cervical

cancer by Pap smear. Participants who choose to undergo sigmoid biopsies may benefit from early detection of lower bowel cancer through the evaluation of suspicious polyps that may be found during these biopsies. Findings of medical concern will be referred for appropriate care and treatment. Others may benefit from knowledge gained in this study that may contribute to the development of an HIV vaccine.

5.6.4. Risks to the Study Personnel and the Environment

The principal risk in the clinical setting is in the handling of needles that may be contaminated and the attendant risks including hepatitis, HIV, and other human pathogens. Adherence to standard operating procedures (SOP) for working with infectious agents and universal precautions will reduce the risk of exposure.

There are no known risks to the environment other than those associated with the generation of biohazardous waste attendant to [vaccination] of humans. All biohazardous waste will be disposed of as stipulated by local, state, and Federal regulations and in accordance with study site SOPs.

5.7. Route of Administration, Dosage Regimen, Treatment Period, and Justification

Participants will be randomized to receive either a full dose of IHV01 (approximately 300 μ g) and A244 (approximately 300 μ g), a fractional dose of IHV01 (approximately 60 μ g) and A244 (approximately 60 μ g), or placebo. Participants in Groups 3 and 4 will receive ALFQ (approximately 0.5ml) as part of the A244 vaccination. Participants will receive 2 IM injections into the quadriceps¹ muscle at Day 0. The same quadriceps muscle will be used for both injections. Participants randomized to receive the vaccines will have one injection of IHV01 and one injection of A244/AHFG at a full or fractional dose with or without ALFQ, whereas participants randomized to receive placebo will get 2 separate injections of Normal Saline. All placebo injection volumes will match the vaccine injection volumes for the group in which a participant has been randomized.

Refer to Section 7.4 and [Table 3](#) for more information.

5.8. Compliance Statement

The study will be conducted according to the protocol and in compliance with ICH GCP, Belmont Principles, and other applicable ethical, regulatory, Federal and DoD requirements. All identified study personnel will be trained to perform their roles and will carry out their responsibilities in accordance with the roles and responsibilities descriptions listed in [Appendix A](#).

¹ Although the IHV01 investigator's brochure notes that injection into the non-dominant deltoid will be used in all cases, the product owner has agreed to allow injections into the quadriceps for RV546. We do not anticipate any safety issues with injection into the quadriceps muscle, which was chosen to help participants tolerate the total injection volume.

5.9. Study Population

A total of 80 healthy, HIV-uninfected participants at a low risk for HIV infection, available for 12 months, who were randomized to receive active vaccine in RV306 and completed all vaccinations will be enrolled. A total of 274/300 (91.3%) active recipients from Groups 2, 3, 4a, and 4b received all vaccinations and completed all study visits in RV306.

Each site will recruit participants who participated in RV306 at their respective sites, however recruitment may also include participants who participated in RV306 at the site in Chiang Mai University if the participant is willing to be enrolled and followed at one of the two Bangkok sites. It is anticipated that up to 110 prior RV306 participants will be screened in order to enroll 80 participants into RV546. As much as possible, an equivalent proportion of male and female participants will be enrolled into each arm of the study.

Study staff and participants will be blinded to vaccine/placebo and full dose/fractional dose assignment. As a byproduct of the sequential enrollment of the vaccine/placebo groups, study staff will not be blinded to a participant's receipt of ALFQ. Groups 1 and 2 (without ALFQ adjuvant) will be enrolled first in a randomized, double-blinded manner. Enrollment into Groups 1 and 2 will begin with no more than two participants per site per week for the first two weeks. Once at least 7-days of safety data is available from the first eight participants enrolled across Groups 1 and 2, the Safety Monitoring Committee (SMC) will review 7-days of safety data from these participants to determine whether enrollment can continue. Enrollment into Groups 1 and 2 will be unrestricted after any safety concerns raised by the SMC are addressed and the Sponsor has given their approval for continuation of enrollment. Enrollment into Groups 3 and 4 will commence after enrollment into Group 1 and Group 2 has been completed, the SMC has reviewed 7-days of safety data from all Group 1 and 2 participants, and the Sponsor gives their approval. Enrollment into Groups 3 and 4 will follow a similar approach with no more than two participants per site per week for the first two weeks, followed by an SMC review of 7-days of safety data from the first eight participants enrolled across both Groups, and Sponsor approval before enrollment can continue unrestricted in Groups 3 and 4. The PI, investigators and study participants will remain blinded to vaccine and placebo allocation.

The legal age at which individuals can provide their own consent to participate in research in Thailand is 18 years. Children will not be recruited for RV546 not only because it does not meet the guidelines for inclusion of children in research, but also because participants must have participated in RV306 to be eligible for RV546. Since the minimum age for eligibility in RV306 was 20 years old at the time of enrollment, all potential participants will legally be considered adults. There are no limitations to race, ethnicity or sex. Refer to Section 12.3 for a statistical justification of the sample size.

5.10. Study Site

All clinical study activities, including mucosal secretion collections, will take place at the Vaccine Trial Center, Faculty of Tropical Medicine at Mahidol University and at the Royal Thai Army Clinical Research Center at the Armed Forces Research Institute of Medical Sciences, both in Bangkok.

Leukapheresis and lymph node biopsy procedures will be completed at the Thai Red Cross AIDS Research Center, Institute of HIV Research and Innovation (IHRI) Foundation and the

RV546/WRAIR #2733/S-19-01
IND #: 27011

The Surgeon General
Department of the Army

Chulalongkorn Memorial Hospital, all in Bangkok. Sigmoid biopsy procedures will only be completed at the Chulalongkorn Memorial Hospital.

6. TRIAL OBJECTIVES AND PURPOSE

6.1. Primary Objective

- To evaluate the safety of 3 novel investigational products in a late vaccine boost setting: the candidate IHV01 and A244/AHFG vaccines and the ALFQ adjuvant

6.2. Secondary Objectives

- To evaluate the effect of a full dose of the IHV01 and A244/AHFG vaccines and the ALFQ adjuvant on cellular, humoral, and innate immune responses (peripheral, lymphoid and mucosal).
- To evaluate the effect of fractional dosing of the IHV01 and A244/AHFG vaccines on cellular, humoral, and innate immune responses (peripheral, lymphoid and mucosal).

7. TRIAL DESIGN

7.1. Study Endpoints

7.1.1. Safety Endpoints

Safety will be assessed both by direct physical examination and by diary cards ([Appendix O](#)), which serve as memory tools for better identification of reactions. Participants will be assessed at a pre-vaccination baseline and will remain in clinic under direct observation for at least 30 minutes post-vaccination. Participants will return to clinic on Days 1 and 7 post-vaccination as per the Schedule of Evaluations (SOE; [Table 3](#)). During these visits, participants will be assessed for symptoms of local (at the injection sites) reactogenicity such as erythema, induration, pain/tenderness, swelling and limitation of leg movement as well as for symptoms of systemic reactogenicity such as fever, tiredness, chills, myalgia, arthralgia, headache, nausea, and rash. After review of the diary card and discussion with the participant, the study staff will document any post-vaccination reaction(s) and all related information (severity, frequency, etc.) concerning such a reaction in the participant's clinic source documents. Results will be expressed as percent of participants with the overall and specific post-vaccination reactions.

AEs and SAEs will be recorded at all visits along with timing and possible attribution to Investigational Product. Because this clinical trial involves an adjuvant, AESIs will also be assessed. Results will be expressed as percent of participants with the AEs and SAEs. Safety laboratory analyses of complete blood count, liver function tests, urinalysis, and pregnancy test in females will also be performed according to the SOE.

7.1.2. Immunogenicity Study Endpoints

Vaccine-induced immune responses will be assessed in study participants as detailed in the SOE ([Table 3](#)).

Humoral responses will be assessed by HIV-specific binding antibody assays, HIV-specific neutralizing antibody assays, and non-neutralizing antibody function assays at Days 0, 14, 168, and 336. Humoral mucosal immune responses in the rectal, semen and cervico-vaginal compartments will be assessed using non-invasive sampling methods (sponge, menstrual disc, and masturbation) at the same time points. Cell-mediated immune responses will be assessed utilizing invasive sigmoid and lymph node biopsies that will be performed at Day 14. Results of immunology assessments through invasive collection methods in the mucosal compartment are exploratory and will be mostly descriptive as performed in a limited number of participants.

Measurement of CD4+ and CD8+ T-cell effector function will be evaluated through response by cytokines such as IFN- γ and IL2. The CD4+ function will be assessed by the lymphoproliferation responses as measured by the functional CFSE assay. Innate immunity (e.g., NK cells) will be assessed by quantifying ADCC and ADCP, determining NK cell phenotype using various flow cytometric panels, cytokine array assays to characterize the type of cytokines elicited by this vaccine regimen with or without adjuvants, by the assessment of gene expression by DNA microarray and related techniques, and other related assays. B-cell responses will be characterized in blood and in diverse anatomical compartments (provided by sigmoid biopsies and lymph nodes biopsies) in a subset of participants. Host gene transcription profile and signature to vaccine antigens will be assessed by RNA sequencing and related techniques.

Leukapheresis will be performed at Day 14 in a subset of willing participants for in-depth investigations of the T-cell responses.

In the context of unknown immune correlates of protection, additional assessments may be performed as new scientific technologies and assessment tools are made available.

For further details, see Section [10.1](#).

7.2. Overall Study Design

The purpose of this Phase I randomized, double-blind, placebo-controlled clinical trial is to define the safety and immunogenicity of IHV01 and A244/AHFG with and without ALFQ at a full dose and at a fractional dose (one-fifth of a full dose) in a late boost setting for participants who had previously received the AIDSVAX® B/E with or without ALVAC in RV306. Blood, lymph nodes, and mucosal specimens will be collected to assess innate, cell-mediated, and humoral immune responses.

A total of 80 healthy, HIV-uninfected previous RV306 participants who were randomized to receive active vaccine with late boosting will be enrolled into this study. Only the RV306 participants who were randomized to receive active investigational product with a late boost in Groups 2, 3, 4a or 4b, and completed all vaccinations, will be eligible for enrollment.

Within each study Group, participants will be randomized to receive 2 IM injections, either IHV01 and A244/AHFG with or without ALFQ or Normal Saline placebo on Day 0 (see [Figure 1](#)) at a targeted ratio of 4:1 vaccine to placebo. Half of the IHV01 and A244/AHFG recipients will receive the full dose (Groups 1 and 3) of each vaccine and the other half will receive a fractional dose (Groups 2 and 4) of each vaccine, which is one fifth of the full dose. Groups 3 and 4 will also receive ALFQ. Once the first eight participants are enrolled across Groups 1 and 2 at a pace of no more than two participants per site per week for the first two weeks, the SMC will review 7-days of safety data from these participants to determine whether enrollment can continue. Any safety concerns raised by the SMC will be addressed prior to the continuation of enrollment. Enrollment into Groups 1 and 2 will continue unrestricted after any safety concerns raised by the SMC are addressed and the Sponsor gives their approval for the continuation of enrollment. Enrollment into Groups 3 and 4 will commence after enrollment into Groups 1 and 2 has been completed, the SMC has reviewed 7-days of safety data from all Group 1 and Group 2 participants, and the Sponsor gives their approval. Enrollment into Groups 3 and 4 will follow a similar approach with no more than two participants per site per week for the first two weeks, followed by an SMC review of 7-days of safety data from the first eight participants enrolled across both Groups, and Sponsor approval before enrollment can continue unrestricted in Groups 3 and 4.

At the screening visit, the participant's general health will be evaluated via medical history, physical exam, pregnancy testing, urinalysis, and testing for HIV, syphilis, and Hepatitis B.

Participants will return for follow-up at 1, 7, 14, 168, and 336 days after vaccination.

Safety and tolerability will be assessed with both clinical and laboratory monitoring. Vaccine-related reactions will be observed and solicited for 30 minutes post-vaccination and with the aid of a diary card and interview of participants during the 7 days post-vaccination. The information gained from the review of the diary card and the interview with the participants will be

documented in the clinical study chart. In addition, AEs will be documented at each clinical encounter. AEs will be graded for seriousness, severity and relationship to the investigational product.

A subset of willing participants will undergo longitudinal mucosal collections for semen, rectal secretions, and/or cervico-vaginal secretions at Days 0, 14, 168, and 336 as well as leukapheresis, sigmoid biopsy, and/or lymph node biopsy at Day 14 as described in the SOE (Table 3). Participants will be followed until 12 months after vaccination for safety and immunogenicity analyses.

Figure 1: Study Group Design

[figure not shown]

Table 3: Schedule of Evaluations

Visit	S1	1 ¹¹	2	3	4	5	6 (Exit)	7
Visit Day	-45 to -16	0	1	7	14	168	336	post database lock
Visit Week		0	1	1	2	24	48	
Visit Month		0			0.5	6	12	
Visit Window			+2d	-/+2d	-2/+3d	-/+7d	-/+7d	
Clinical								
Informed Consent (Main, Storage/Future Use, Genetic, and Optional Procedures)	X							Final Results and Unblinding ⁵
Test of Understanding	X							
Enrollment and Randomization		X						
Vaccination		X						
Vital Signs ⁸ and Physical exam ¹	X	X		X	X	X	X	
Medical History & Concomitant Medications	X	X		X	X	X	X	
Adverse Event Documentation (AE, SAE, AESI)		X	X	X	X	X	X	
Diary Card		X	X	X				
HIV Risk Assessment/Risk Counseling	X	X			X	X	X	
Pregnancy Test & Pre/Post Counseling	X	X			X	X	X	
Urinalysis (blood, protein and glucose)	X	X	X	X	X	X	X	
CBC w/ diff & CD4	2	2	2	2	2	2	2	
Creatinine, ALT/AST	3.5			3.5	3.5	3.5	3.5	
Syphilis and Hepatitis B Serology	3.5							
HIV Testing & Pre/Post Counseling ⁹	6				6	6	6	
Optional Procedures								
Mucosal Secretions ^{2,7} ; Plasma LH and FSH (cervical secretions only)		X			X	X	X	
STI Testing ⁷	X							
Vaginal ^{2,7} and/or rectal ^{3,7} and/or penile ⁷ swab for microbiome and proteome		X			X	X	X	
Endocervical Cytobrush/swab ^{2,7}		X			X	X	X	
Pap Smear, if none available in last two years ⁷	X							
Sigmoid Biopsy ^{3,7}					X			

Visit	S1	1 ¹¹	2	3	4	5	6 (Exit)	7
Visit Day	-45 to -16	0	1	7	14	168	336	post database lock
Visit Week		0	1	1	2	24	48	
Visit Month		0			0.5	6	12	
Visit Window			+2d	-/+2d	-2/+3d	-/+7d	-/+7d	
Lymph Node Biopsy					X			
Leukapheresis ⁴					X (10ml)			
Safety Tests for Biopsy or Leukapheresis (up to max possible volume) ¹⁰					20			
Research								
HIV Binding Antibody		SP			SP	SP	SP	
HIV Neutralizing Antibody Assays		6			6	6	6	
Functional Antibody Assays		SP			SP	SP	SP	
B-Cell Analysis ⁶		30		30	30	30	30	
Multiparameter Flow Cytometry		20			20	20	20	
Innate Cell Analysis		20	20	20	20	20	20	
Transcriptomics		20	20	20	20	20	20	
Additional Immunogenicity Testing ⁶		30		30	30	30	30	
Daily Volume (mL)	15	128	42	105.5	157.5	137.5	137.5	
Daily volume (mL) for participant weighing below 50 kgs	15	93	42	70.5	122.5	137.5	137.5	
Cumulative Volume (mL)	15	143	185	290.5	448	585.5	723	
Cumulative Volume (mL) for participant weighing below 50 kgs	15	108	150	220.5	343	480.5	618	
12-Week Cumulative Volume (mL)⁶					448	137.5	137.5	
12-Week Cumulative Volume (mL) for participant weighing below 50 kgs⁶					343	137.5	137.5	

SP = Assay performed from stored plasma, no additional blood volume required

¹ Full physical examination at screening (Visit S1) and targeted physical examination at all other visits.

² FGT questionnaire (Appendix J) will be administered to all participants who choose to undergo mucosal secretion collections and/or endocervical cytobrush/swab for microbiome/proteome assessment and cell collection prior to procedure at each collection visit

³ Gastrointestinal and dietary questionnaires (Appendix I & Appendix K) will be administered to all participants who choose to undergo a sigmoid biopsy and/or rectal swab for microbiome/proteome assessment prior to the procedure at each collection visit

⁴ Participants undergoing leukapheresis at Visit 4 will not have peripheral blood drawn for B-cell analysis, multiparameter flow cytometry, innate cell analysis, transcriptomics, or additional immunogenicity testing. In addition to the blood drawn for the remaining tests on the SOE, 8.5ml of blood will be collected by phlebotomy for PBMC and plasma storage. Red blood cell loss from leukapheresis is estimated to be 10mL.

⁵ Participants will be contacted for the unblinding visit after the clinical data is locked.

⁶ The blood volumes drawn are in accordance with the Thai National Blood Bank policy: donation every 3 months but no more than 4 times a year; the amount of blood for each donation is according to weight that applies to both male and female: >50 Kg, 450 mL; ≤50 Kg, 350 mL. For participants who weigh below 50 Kg, blood for “Additional Immunogenicity Testing” will not be collected at Visits 1, 3 and 4 and only 25 mL of blood will be collected for “B-Cell Analysis” at Visits 1, 3, and 4.

⁷ Participants who consent for optional mucosal collections (semen, penile, rectal, and cervico-vaginal secretions, and cytobrush) and sigmoid biopsies will undergo additional testing for gonorrhea/chlamydia genital infections. Female participants who consent for optional mucosal collections will also undergo a pelvic examination that includes a Pap smear (if not done in 2 years prior to the mucosal collection) and visual inspection to evaluate for abnormalities. Female participants who choose to self-insert the menstrual disc collection device will be given instructions for self-insertion ([Appendix T](#)). Male participants who consent for optional mucosal collections will undergo a brief visual examination at the screening visit to assess the presence of urethral inflammation and will be given instructions for self-collection ([Appendix U](#)). Abnormalities that affect the participant’s safety or welfare or those that would increase the risk to a participant will preclude their participation in optional procedures.

⁸ Vitals to be collected both pre- and at about 30 minutes post-vaccination at Day 0.

⁹ Due to the time required to receive results of HIV testing, post-test counseling will occur at the next study visit after the results are available. HIV testing will be completed as described in Section [11.1.4.4](#) and management of positive results will be as described in Section [9.5](#).

¹⁰ Up to 10mL of blood will be drawn for safety tests within 2 days before the biopsy procedures for safety purposes. For the leukapheresis procedure, up to 10mL of blood will be drawn for safety tests within 2 days before and after the procedure for a total of 20mL of blood collected across both blood draws.

¹¹ Repeat testing that is necessary to establish a participant’s eligibility will not affect the post-screening enrollment window unless the repeat testing is necessary to establish a baseline CD4 count, in which case enrollment will occur no sooner than 16 days after the date that blood was drawn for the baseline CD4 count.

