- Mucosal secretion collection, plasma LH and FSH (cervical secretions only) and Female Genital Tract (FGT) Questionnaire (Days 0, 14, 168 and 336)
- Endocervical cytobrush/swab and FGT Questionnaire (Days 0, 14, 168 and 336)

At intervals specified in the SOE, blood will be drawn for safety and immunologic assays. For participants who weigh >50 kg, the total blood volume drawn from each participant will not exceed 450 mL in any 12-week period. For participants who weigh ≤ 50 kg, the total blood volume drawn from each participant will not exceed 350 mL in any 12-week period.

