9.1.5. Leukapheresis

Leukapheresis will be performed only at Visit 4 on participants who provide separate informed consent for the procedure. The procedure will be performed by trained personnel at the King Chulalongkorn Memorial Hospital, the Thai Red Cross AIDS Research Centre, or the Institute of HIV Research and Innovation (IHRI) Foundation.

For the leukapheresis procedure, participants will be connected to a cell separator machine via IV, which will separate white blood cells for laboratory testing while returning red blood cells either through the same needle or through a second needle placed in the opposite arm. When the procedure is completed, the maximum total red blood cell loss is about 10 mL (less than one tablespoon). Participants who undergo the leukapheresis procedure will not have blood drawn for immunogenicity assays at Visit 4. In addition to the white blood cells that are collected, approximately 150 mL of plasma will be removed at the end of each leukapheresis procedure for storage. Participants who undergo leukapheresis will have blood collected by phlebotomy in accordance with the SOE ([Table 3](#)), however they be exempted from the immunogenicity blood draw scheduled at the same visit. An additional 8.5ml of blood will be collected from these participants for PBMC and plasma storage in order to have comparator cells from each visit. Leukapheresis will be performed on participants whose platelet counts or hemoglobin counts meet the protocol inclusion criteria.

The entire procedure will take up to 2-3 hours, during which time the participant will be under constant observation by trained leukapheresis staff. If tingling in the face, lips or hands is experienced, study staff may offer calcium carbonate tablets to correct the calcium loss. Leukapheresis can occasionally cause nausea and may temporarily lower platelet count. More rarely, vomiting, fainting, seizures, dizziness, muscle cramps, itching, flushing, or burning sensation, rash, swelling of hands and feet, headache, nasal congestion, sneezing, wheezing, or chest tightness can occur. After the procedure is complete, participants will be observed for 30 minutes.

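### At exactly 50 kg the 350 mL cap applies but the reduced draw does not: without leukapheresis, Table 3 schedules 428 mL or more by Visit 4

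*Protocol*

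**What the plan says.** Footnote 6 to Protocol Table 3 (Section 7.2) adopts the Thai National Blood Bank limits: 450 mL for weight above 50 kg and 350 mL for weight of 50 kg or less. Section 9.1.1 restates the lower limit as a rule of the trial: for participants of 50 kg or less the total "will not exceed 350 mL in any 12-week period".

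The reduction that serves the lower limit is in the second part of footnote 6. "For participants who weigh below 50 Kg", the Additional Immunogenicity Testing sample is omitted at Visits 1, 3 and 4, and the B-cell sample is 25 mL instead of 30 mL at the same visits. Three rows of Table 3 carry the same strict threshold: "Daily volume (mL) for participant weighing below 50 kgs", the matching cumulative row, and "12-Week Cumulative Volume (mL) for participant weighing below 50 kgs". SAP Table 2 reproduces these rows for reference.

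Three other provisions affect the Visit 4 total:

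- Footnote 4: "Participants undergoing leukapheresis at Visit 4 will not have peripheral blood drawn for B-cell analysis", nor for the other large research samples. They give 8.5 mL for storage instead, and red-cell loss is put at 10 mL.
- Footnote 10: "Up to 10mL of blood will be drawn for safety tests within 2 days before the biopsy procedures". For leukapheresis the allowance is 10 mL before and 10 mL after.
- Section 9.1.5: "approximately 150 mL of plasma will be removed at the end of each leukapheresis procedure for storage". Table 3 does not count this plasma.

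**The concern.** The cap includes 50 kg and the reduction excludes it. Nothing else in the protocol assigns the reduced draw to that weight. Read literally, a 50 kg participant is limited to 350 mL and is also on a schedule whose stated 12-week total is 448 mL.

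A site cannot follow both instructions. If it draws what Table 3 lists, it exceeds a limit that the protocol takes from national blood bank policy. If it respects Section 9.1.1, it must leave out scheduled research tubes, and the text does not say which ones at that weight.

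What is at stake is conformity with the blood-volume limit and a clear instruction to the sites, not the validity of any comparison.

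**Working it through.** **Inputs.** All volumes are in mL and come from Protocol Table 3, with footnotes 4, 6 and 10.

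**1. Reproduce the plan's totals.**

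- Screening: 2 + 3.5 + 3.5 + 6 = 15
- Visit 1: 2 + 6 + 30 + 20 + 20 + 20 + 30 = 128
- Visit 2: 2 + 20 + 20 = 42
- Visit 3: 2 + 3.5 + 30 + 20 + 20 + 30 = 105.5
- Visit 4 without safety tests: 2 + 3.5 + 6 + 6 + 30 + 20 + 20 + 20 + 30 = 137.5
- Visit 4 with the 20 mL maximum for safety tests: 157.5

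Screening to Visit 3 is 15 + 128 + 42 + 105.5 = 290.5. Adding 157.5 gives 448, the stated full total. The reduction is 30 + 5 = 35 at each of Visits 1, 3 and 4, so 105 in all, and 448 − 105 = 343, the stated reduced total. Both figures reproduce exactly.

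**2. Do these draws share one 12-week window?** The earliest screening day is −45. Visit 4 is Day 14 with a window to +3, so Day 17 at the latest. The span is 45 + 17 = 62 days, inside 84.

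**3. Exactly 50 kg, without leukapheresis, on the schedule as written.**

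| Optional procedures | Total (mL) | Over 350 mL |
|---|---|---|
| None | 290.5 + 137.5 = 428 | 78 (22.3%) |
| One 10 mL pre-biopsy draw | 438 | 88 (25.1%) |
| Two separate pre-biopsy draws (the table's 20 mL maximum) | 448 | 98 (28.0%) |

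Leaving out the screening draw, the first row is still 428 − 15 = 413, which is 63 over.

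**4. Exactly 50 kg, with leukapheresis.** Footnote 4 removes 30 + 20 + 20 + 20 + 30 = 120 from Visit 4. On the table's own counting the total is 290.5 + (137.5 − 120) + 20 safety tests + 8.5 storage + 10 red-cell loss = 346.5, just inside the cap. This depends on the counting convention. Section 7.2 allows "leukapheresis, sigmoid biopsy, and/or lymph node biopsy at Day 14", and one separate pre-biopsy draw on top would give 356.5. Counting the plasma would give about 346.5 + 150 = 496.5. The finding is therefore confined to participants without leukapheresis.

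**5. Exactly 50 kg, if the reduced draw applied.** Without leukapheresis: 428 − 105 = 323, 438 − 105 = 333 and 448 − 105 = 343, all within 350. With leukapheresis only the reductions at Visits 1 and 3 remain to be made (2 × 35 = 70), giving 346.5 − 70 = 276.5, or 286.5 with one separate pre-biopsy draw, or about 276.5 + 150 = 426.5 if plasma is counted.

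The totals omit draws for which no volume is stated (LH/FSH with cervical secretions, and repeat tests). These can only add to them.

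**The case against.** The strongest reply is that Section 9.1.1 already forbids the excess. Its cap expressly includes 50 kg, and a row label does not override an express limit. The protocol also holds only two schedules, 448 mL under the 450 mL cap and 343 mL under the 350 mL cap, so a sensible site would use the second at 50 kg. A Clinical MOP is mentioned in Section 9.6 and may say so. On this view the point is a wording slip with almost no practical reach.

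Much of this is fair. It probably is a slip, and one ready-made reduced schedule does fit, so a site is not left without a natural choice. But the cap conflicts with the schedule and does not repair it: the text that names the tubes to drop restricts that instruction to weights under 50 kg. A site using the reduced schedule at 50 kg would be departing from footnote 6 to comply with Section 9.1.1.

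The 448 mL figure is also open to challenge. Footnote 10 can be read as one draw of up to 10 mL covering both biopsies, which makes 438 mL the maximum without leukapheresis. Similarly, 356.5 mL goes beyond the 20 mL that Table 3 labels as the maximum for safety tests, and 496.5 mL adopts a plasma convention that the protocol does not use. The finding rests on none of these; it rests on 428 mL, which needs no optional procedure.

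**Conclusion.** The concern holds. For a participant recorded at exactly 50 kg who does not have leukapheresis, the schedule as written exceeds the protocol's own 12-week limit by at least 78 mL. The conclusion assumes that Table 3 and footnote 6 are applied literally and that the tabulated volumes are drawn in full.

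The matter is minor. It concerns one boundary weight, and the documents do not say how precisely weight is recorded, so the number affected cannot be estimated. Whether leukapheresis plasma should count toward the cap is a separate question that this finding does not settle.

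**What to change.** In Protocol Table 3, change the threshold for the reduced draw from under 50 kg to 50 kg or less, in footnote 6 and in the three row labels (daily, cumulative and 12-week cumulative). Edit SAP Table 2 to match; that is for consistency only, since the SAP directs no draws. At the new maximum of 343 mL the headroom is 7 mL, from which LH/FSH and repeat tests would also have to come.

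The cost is a minor modification needing sponsor and IRB approval before use (Section 15.1.2); it could go in with the next amendment. Each affected participant gives up to 105 mL less research blood: three Additional Immunogenicity Testing samples of 30 mL, and 5 mL of B-cell blood at each of Visits 1, 3 and 4. With leukapheresis the loss is 70 mL. SAP Section 4.4.2 says randomization into Groups 1 and 2 has stopped, so for new enrolments the change can reach only Groups 3 and 4.
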